#### 17.3.1 Primary analysis for the primary estimand

The primary estimand will be estimated based on the FASpregnant using data from the last planned visit prior to delivery after GW 16. Hence, data assessed at the planned visit prior to delivery will be used in the analysis, provided the visit corresponds to the GW 16 visit or later. If delivery is in GW 40, data from GW 36 will be used. If data at this visit is missing, and data from an additional visit after GW 36 and prior to delivery is available, data from this visit will be used. Similarly, if delivery is in week GW 18, data from GW 16 will be applied. If data at this visit is missing, and data from an additional visit after GW 16 and prior to delivery is available, data from this visit will be applied. Available data from the in-trial period will be included regardless of whether trial product was discontinued or not.

The primary statistical analysis will be using multiple imputations to handle missing data assuming that the missing data mechanism is missing at random (MAR) within the groups used for imputation.

Imputation of missing data will be done within four groups of subjects defined by randomised treatment arm and whether or not subjects discontinue treatment. It is hereby assumed that the likely values of what the missing data would have been if available, are best described by information

Protocol  
 Trial ID: NN1250-4300  
 UTN: U1111-1191-3018  
 EudraCT no.: 2017-000048-17

~~CONFIDENTIAL~~

Date: 17 December 2020  
 Version: 4.0  
 Status: Final  
 Page: 87 of 110

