### **Analysis used for confirming non-inferiority of IDeg versus IDet**

For each of the 1000 imputed datasets last planned HbA1c prior to delivery after GW 16 will be analysed using an ANCOVA with treatment, region and the stratification factor as categorical fixed effects and a pregnancy status at randomisation-by-baseline HbA1c interaction. In each analysis the treatment difference between IDeg and IDet and the associated standard error will be estimated. The estimates and standard errors from the 1000 datasets are pooled to one estimate and associated standard errors using Rubin's rule to draw inference. From these pooled estimates the 95% CI for the treatment difference is calculated.

Non-inferiority will be considered confirmed if the upper bound of the CI is strictly below 0.4%. The p-value corresponding to a two-sided test of no difference will also be reported.

Data from the in-trial pregnancy and post-pregnancy periods will be summarised and plotted by treatment arm and visits based on FASpregnant. Summaries and plots will also be presented separately for subjects randomised as pregnant and subjects randomised as non-pregnant.

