## 5 Review procedure

Surveillance of titration data will be performed centrally by Novo Nordisk in an unbiased manner. It is important that data regarding dose titration is entered into the eCRF within 24 hours (on weekdays). If delays occur, action cannot be taken in due time before the subject's next site visit or phone contact. The aim is to reduce the time periods in which a subject may receive suboptimal treatment.

The data listed in Section [4](#) will be reviewed by Novo Nordisk within 24 hours (on weekdays). The reviewer may contact the investigator to get clarification regarding the reason for deviation or to request entry of missing data.

When the investigator receives an inquiry, a response should be received at Novo Nordisk within 24 hours (on weekdays).

During the trial, HbA1c will be monitored by Novo Nordisk for additional surveillance of the glycaemic control. Novo Nordisk may be in contact with sites (visit or phone contact) to discuss progress in glycaemic control and titration of individual subjects based on SMPGs and HbA1c. This will be done in an unbiased and whenever possible in a blinded manner.

Protocol Appendix A  
Trial ID: NN1250-4300  
UTN: U1111-1191-3018  
EudraCT no.: 2017-000048-17

CONFIDENTIAL

Date: 17 December 2020  
Version: 4.0  
Status: Final  
Page: 7 of 7

Novo Nordisk

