**Novo Nordisk**

## **Imputation :**

Step 1: Imputation of missing data will be done within four groups of subjects defined by randomised treatment arm and whether or not subjects discontinue treatment. It is hereby assumed that the likely values of what the missing data would have been if available, are best described by information from subjects who at the last scheduled visit prior to delivery are similar in terms of randomised treatment arm and whether or not treatment has been discontinued.

If there are 3 or less retrieved observations among discontinued subjects in a treatment group, it is infeasible to estimate a simple intercept model (including variance) and imputed separately by on-treatment and off-treatment. Instead, on-treatment factors will be included in the models. Hereby, separate means will be estimated for on-treatment and off-treatment observations, while only one joint variance is estimated. In the special case with no subjects off-treatment having HbA1c in one treatment group, an on-treatment factor will not be included in the this group but only in the other group (expecting that this group also has most missing values).

Missing data at the last scheduled visit prior to delivery after GW 16 are for each group imputed in the following steps:

An analysis of covariance (ANCOVA) will be fitted to the observed last values of last HbA1c prior to delivery after GW 16

- For subjects where HbA1c at the last scheduled visit prior to time of delivery is in the on-treatment period, the model will include region and the stratification factor as categorical fixed effects, and a pregnancy status at randomisation-by-baseline HbA1c interaction.
- For subjects where HbA1c at the last scheduled visit prior to time of delivery is not in the on-treatment period, the model will include pregnancy status at randomisation and a pregnancy status at randomisation-by-baseline HbA1c interaction. If this model cannot be fitted in case of very few retrieved observations among discontinued subjects, a model including pregnancy status at randomisation will be applied. If this model cannot be fitted either, a simple model including just the intercept will be fitted instead. If there are 3 or less retrieved observations among discontinued subjects in one or both treatment groups, this step will be skipped.

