- With 3 or less retrieved observations among discontinued subjects in one of the treatment groups, the step below replaces the two steps above. For subjects with HbA1c at the last scheduled visit prior to time of delivery, the model will include on-treatment (Yes/No), region and the stratification factor as categorical fixed effects, and a pregnancy status at randomisation-by-baseline HbA1c interaction. In treatment groups having no subjects off-treatment with HbA1c, the on-treatment factor will not be included.

The estimated parameters from the analysis of covariance together with the variances of the estimates will be used to simulate 1000 data sets with imputed last planned HbA1c prior to delivery after GW 16 data for subjects missing these. Each of the 1000 datasets use one set of estimated

Statistical Analysis Plan  
 Trial ID: NN1250-4300  
 UTN: U1111-1191-3018  
 EudraCT No: 2017-000048-17

~~CONFIDENTIAL~~

Date: 27 January 2021  
 Version: 2.0  
 Status: Final  
 Page: 19 of 34

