#### Imputation :

Step 2 : Impute the missing value by fitting enriched ancova model to the observed last values of last HbA1c prior to delivery after GW 16. Imputation was done within randomised treatment arm and model will be fitted with the categorical fixed effects, factor and interaction term in the same order as mentioned in [Table 5-3](#). Similar to the description above for the primary estimand the estimated parameters from the ANCOVA together with the variances of the estimates will be used to simulate 1000 data sets with imputed last planned HbA1c prior to delivery after GW 16 data for subjects missing these.

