**Novo Nordisk**

- If the difference of the visit date and the delivery date was  $\leq 35$  days (28 days between scheduled site visits + 7 days visit window = 35 days), LPVISPD L is set to the last visit.
- If the difference of the visit date and the delivery date was  $> 35$  days, LPVISPD L is set to the following planned site visit 4 weeks later.

**Step 4:** For subjects registered to miss site visit 79 due to the Covid-19 pandemic, LPVISPD L is set to 79.

**Step 5:** For subjects withdrawing from trial before GW16 without further information, delivery is assumed to be after GW16 and LPVISPD L is set to 79.

Hence, data assessed at the planned visit prior to delivery will be used in the analysis, provided the visit corresponds to the visit on or after GW 16.

Statistical Analysis Plan  
Trial ID: NN1250-4300  
UTN: U1111-1191-3018  
EudraCT No: 2017-000048-17

~~CONFIDENTIAL~~

Date:	27 January 2021	Novo Nordisk
Version:	2.0	
Status:	Final	
Page:	34 of 34	

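### SAP Table 5-3 lists region names as the stratification levels of the secondary-estimand imputation model, and no imputation or sensitivity analysis uses HbA1c measured from GW 16 up to the landmark visit

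*SAP*

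**What the plan says.** **Primary estimand (SAP 5.3.2.1, Protocol 17.3.1).** Imputation is by arm and by whether treatment was discontinued. For on-treatment women, "the model will include region and the stratification factor as categorical fixed effects, and a pregnancy status at randomisation-by-baseline HbA1c interaction". Discontinuers get a smaller model built from pregnancy status and baseline HbA1c, with simpler versions if data are sparse. If an arm has three or fewer retrieved values, a pooled model replaces both: "the model will include on-treatment (Yes/No), region and the stratification factor as categorical fixed effects", plus the same baseline interaction. The protocol assumes that the "missing data mechanism is missing at random (MAR) within the groups used for imputation".

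**Secondary estimand (SAP 5.3.2.2).** Step 2 begins "Impute the missing value by fitting enriched ancova model to the observed last values of last" and sends the reader to Table 5-3. That table has three rows: region, stratification factor, and pregnancy status with treatment-baseline HbA1c.

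**Landmark visit (SAP 6.3.1.1).** When delivery comes more than 35 days after the last attended visit, the landmark "is set to the following planned site visit 4 weeks later". "For subjects registered to miss site visit 79 due to the Covid-19 pandemic", it is set to visit 79.

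**Data on file.** Protocol flowchart 2.3 schedules HbA1c at every site visit from GW 16 to GW 36. Under Appendix A, section 5, HbA1c "will be monitored by Novo Nordisk for additional surveillance of the glycaemic control".

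**Sensitivity analyses (SAP 5.3.3).** There are two: the same imputation in the per-protocol set, and a tipping-point analysis that adds a penalty, in steps of 0.5, to the imputed IDeg values. SAP 5.4.1.1 plans none for the endpoints HbA1c ≤ 6.0% and ≤ 6.5%, although both are formed from these imputations.

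**The concern.** There are two separate matters.

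First, Table 5-3 is the specification a programmer would follow for the secondary estimand, and its stratification row does not contain the stratification factor. Step 2 also calls the model *enriched*, yet nothing in the table enriches it, so it is unclear whether a term was intended and lost.

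Second, a woman whose landmark value is missing is imputed from her treatment baseline and group, even when later HbA1c values are on file. The SAP's own landmark rules produce such cases. If missingness depends on HbA1c during pregnancy, and does so differently by arm, the missing-at-random assumption within groups fails and the comparison can be biased in either direction. In an open-label trial with HbA1c monitored during conduct this is plausible, but nothing in the documents shows it.

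**Working it through.** **Stratification levels, side by side**

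| Place | Levels given for the stratification factor |
|---|---|
| Protocol 17; SAP Tables 5-2 and 5-4 | Four: pregnancy status at randomisation crossed with planned CGM use |
| SAP Table 5-3 | Four place names: Europe, Asia, North America, Oceania |

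The place names do not match the trial's regions either. The region row just above them includes South America and combines Asia with Oceania. Read literally, women from Argentina and Brazil have no level, region enters twice in conflicting forms, planned CGM use drops out, and pregnancy status acts only through the baseline HbA1c interaction.

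**The plan's own figures.** With margin 0.4, SD 0.85, one-sided 2.5% and 80% power, a noncentral-t calculation gives 72 per arm, so 144 in total. Then 144/0.9 = 160 and 144/0.81 = 177.8, rounded up to 178, as in Tables 17-1 and 17-2. Expected discontinuation is 0.8 × 10% + 0.2 × 15% = 11%, consistent with the protocol's upper limit of 12%. Of 178 pregnant women, 178 × 0.9 = 160.2 deliver after GW 16, about 80 per arm.

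**Assumptions, not in the documents**
- Residual correlation of an earlier HbA1c with GW 36 is 0.7^lag (low) or 0.5 + 0.5 × 0.7^lag (high), with lag counted in visits. At one visit (4 weeks) this is 0.70 or 0.85; at five visits (20 weeks), 0.17 or 0.58.
- Dropout depends on the last observed residual (log-odds 0.45 or 0.75 per SD). Women with missing values are then 0.13–0.42% higher at the landmark, in one arm only.
- Baseline correlation is 0.4, and 80% of women are randomised pregnant.

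**First-order size.** Bias in D (IDeg − IDet) ≈ share missing × excess. A negative bias favours non-inferiority.
- Secondary estimand, 12%: 0.12 × 0.13 = 0.016 and 0.12 × 0.42 = 0.050.
- Primary estimand, on-treatment women, an assumed 2%: 0.02 × 0.13 = 0.003 and 0.02 × 0.42 = 0.008.

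**Simulation** (4000 trials per scenario, 50 imputations, 80 per arm, SD 0.85, six visits)

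| Scenario | Current model | Visit-sequential |
|---|---|---|
| 12% missing, IDeg-only drift | −0.017 to −0.050 | −0.002 to +0.001 |
| 12%, high case, a third of missing women without a value from GW 16 on | −0.048 | −0.018 |

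IDet-only drift (high case, 12%) gives +0.049 under the current model. Equal drift in both arms cancels to within 0.001. A single pooled slope on the latest value over-corrects at 12% (+0.008 to +0.013), so each earlier visit needs its own regression. At 2% missing the current model's one-sided type I error is 2.4%, against a nominal 2.5%.

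**Dichotomised endpoints at 12%** (assumed mean 6.4%, IDeg-only drift). The simulated bias in the responder difference is +0.7 to +1.9 points for ≤ 6.0% and +0.8 to +2.3 points for ≤ 6.5%. The visit-sequential version stays within 0.3 points. A rough check multiplies share missing, normal density at the cut-off and excess. For ≤ 6.0%, 0.12 × 0.420 × (0.13 to 0.42) = 0.7 to 2.1 points; for ≤ 6.5%, 0.12 × 0.466 × (0.13 to 0.42) = 0.7 to 2.3 points.

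**Precision.** With partial correlation r, the variance factor moves from 1/(1 − m) to (1 − r²)/(1 − m) + r². At m = 0.12 and 160 women the SE goes from 0.1433 to 0.1425 (r = 0.3) or 0.1390 (r = 0.7). The simulated gain without drift is 0–3% of the SE.

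**The case against.** A reader might infer that the confirmatory test is compromised, because the protocol expects 6% missing data for the primary estimand and the decision rule is "Non-inferiority will be considered confirmed if the upper bound of the CI is strictly below 0.4" (per cent HbA1c). The documents do not support that. The 6% are women who discontinued treatment and were not retrieved. They are imputed from the retrieved-dropout model, or from the pooled fallback with its on-treatment factor. Neither model was simulated here. What remains is on-treatment women with a missing landmark value, and the documents give no count of them.

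The tipping-point analysis also already tests the direction that favours non-inferiority. One 0.5 step exceeds the largest assumed IDeg drift of 0.42: at 12% missing it moves D by 0.12 × 0.5 = 0.06, against a worst simulated bias of 0.050. This stands for the continuous endpoint under both estimands. It does not extend to the dichotomised endpoints or to IDet drift, though IDet drift works against non-inferiority.

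Other limits also stand. The visit-sequential result is partly built in, because simulated dropout depends on values that this model conditions on. Covid-missed visits are administrative, with no stated link to HbA1c. Women who withdraw before GW 16 have no usable value. The 12% case belongs to an estimand that carries no confirmatory decision.

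A reader might also infer from Table 5-3 that the analysis itself will be wrong. The correct levels appear in three other places, so a transcription slip is the likelier explanation. It still needs correcting, since it sits in the table that Step 2 tells the programmer to use.

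**Conclusion.** The stratification row of Table 5-3 is wrong as written. Its numerical effect cannot be derived from the documents.

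The omission of HbA1c between GW 16 and the landmark is a modest gap, worth a sensitivity analysis but not a change to the main models. For the secondary estimand at its 12% upper limit, the bias is about 0.02–0.05% HbA1c. This rests on the assumed one-arm drift of 0.13–0.42% and on the assumed between-visit correlations. For the primary estimand the effect is probably negligible: 0.003–0.008% at an assumed 2% missing, or at most 0.008/0.4 = 2% of the margin, with no type I error inflation. The clearest gain is for the two dichotomised endpoints, which have no planned sensitivity analysis.

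**What to change.** 1. In Table 5-3, replace the stratification categories with the four pregnancy-status-by-CGM levels of Table 5-4. In 5.3.2.2 Step 2, define *enriched* or delete it. This is one table row and one word.
2. Keep the main models. Before database lock, prespecify one within-arm sensitivity analysis that imputes visit by visit (GW 16, 20, 24, 28, 32, 36) up to each woman's own landmark. Each visit is regressed on the current terms plus her on-treatment HbA1c at earlier visits from GW 16 on, then analysed and pooled as now. Starting at GW 16 respects the statement in Protocol 17 that earlier visit data are not used.
3. Apply it to the secondary estimand and to the ≤ 6.0% and ≤ 6.5% endpoints. For the primary estimand, apply it only to on-treatment women with a missing landmark value, and leave the retrieved-dropout and pooled-fallback models as written. Women with no value from GW 16 on before the landmark keep the current model.

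The cost is extra programming and an entry in SAP Appendix 2. No new data are needed and the confirmatory model is unchanged.

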**Novo Nordisk**

mean parameters and estimate of the residual variation. For subjects who have discontinued treatment and where retrieved last planned HbA1c prior to delivery after GW 16 data are not available, it may not be known whether time of delivery is after GW 16. In this case time of delivery will be assumed to be after GW 16 and last planned HbA1c prior to delivery after GW 16 will hence be imputed.

**Analysis:**

Step 2: For each of the 1000 complete datasets, the mean difference in last planned HbA1c prior to delivery after GW 16 will be analysed in both arms using the main ANCOVA model with treatment, region and the stratification factor as categorical fixed effects and a pregnancy status at randomisation-by-baseline HbA1c interaction.

**Pooling:**

Step 3: The estimates and standard errors from the 1000 datasets are pooled to one estimate and associated standard errors using Rubin’s rule to draw inference. From these pooled estimates the 95% CI for the treatment difference is calculated.

The multiple imputations will be generated using Novo Nordisk trial number 12504300 as seed number.

**Table 5-2 Factors and covariates for the main analysis of the primary endpoint for primary estimand**

Factors and covariates at baseline	Type	Categories
Randomised treatment	Categorical fixed effect	IDeg, IDet
Region	Categorical fixed effect	Europe (Austria, Denmark, Greece, Ireland, Italy, United Kingdom and Serbia), North America (Canada), South America (Argentina and Brazil) and Asia/Oceania (Australia, Israel and Russia).
Stratification factor	Categorical fixed effect	Randomised as pregnant and planned continuous use of CGM, randomised as pregnant and no planned continuous use of CGM, randomised as non-pregnant and planned continuous use of CGM, randomised as non-pregnant

Statistical Analysis Plan  
 Trial ID: NN1250-4300  
 UTN: U1111-1191-3018  
 EudraCT No: 2017-000048-17

~~CONFIDENTIAL~~

Date: 27 January 2021  
 Version: 2.0  
 Status: Final  
 Page: 20 of 34

**Novo Nordisk**

		and no planned continuous use of CGM
Pregnancy status at randomisation and treatment baseline HbA 1c	Interaction factor	Treatment baseline for HbA 1c for randomised pregnant , Treatment baseline for HbA 1c for randomised non-pregnant

\*Baseline refers to treatment baseline

The categorical fixed effects and interaction factors will be included in the model as main effects in an additive structure.

Non-inferiority will be considered confirmed if the upper bound of the CI is strictly below 0.4%. The p-value corresponding to a two-sided test of no difference will also be reported.

### 5.3.2.2 Analysis for secondary estimand

The secondary estimand will be estimated based on the FASpregnant using data from the last planned visit prior to delivery after GW 16. Imputation of missing data will now be done within two groups of subjects defined by randomised treatment arm. It is hereby assumed that the likely values of what the missing data would have been if available, are best described by information from subjects who at the last scheduled visit prior to delivery are similar in terms of randomised treatment arm and who have not discontinued treatment.

Missing data at the last scheduled visit prior to delivery after GW 16 are for each group imputed using multiple imputation approach in the following steps:

#### Data preprocessing:

Step 1 : Data retrieved outside of the on-treatment period will not be used in the analysis, but will be considered missing.

#### Imputation :

Step 2 : Impute the missing value by fitting enriched ancova model to the observed last values of last HbA1c prior to delivery after GW 16. Imputation was done within randomised treatment arm and model will be fitted with the categorical fixed effects, factor and interaction term in the same order as mentioned in [Table 5-3](#). Similar to the description above for the primary estimand the estimated parameters from the ANCOVA together with the variances of the estimates will be used to simulate 1000 data sets with imputed last planned HbA1c prior to delivery after GW 16 data for subjects missing these.

#### Analysis:

Statistical Analysis Plan  
 Trial ID: NN1250-4300  
 UTN: U1111-1191-3018  
 EudraCT No: 2017-000048-17

**CONFIDENTIAL**

Date: 27 January 2021  
 Version: 2.0  
 Status: Final  
 Page: 21 of 34

**Novo Nordisk**

Step 3 : For each of the 1000 complete datasets, the mean difference in last planned HbA1c prior to delivery after GW 16 will be analysed in both arms using the main ANCOVA model with factors and covariates as mentioned in [Table 5-4](#).

**Pooling :**

Step 4 : The estimates and standard errors from the 1000 datasets are pooled to one estimate and associated standard errors using Rubin’s rule to draw inference. From these pooled estimates the 95% CI for the treatment difference is calculated.

**Table 5-3 Factors and Covariate for imputation model for secondary estimand**

Factors and covariates	Type	Categories	Order
Region at baseline	Categorical fixed effect	Europe (Austria, Denmark, Greece, Ireland, Italy, United Kingdom and Serbia), North America (Canada), South America (Argentina and Brazil) and Asia/Oceania (Australia, Israel and Russia).	1
Stratification factor at baseline	Categorical fixed effect	Asia, Europe, North America, Oceania	2
Pregnancy status at randomisation, baseline HbA 1c	Interaction factor	Not applicable	3

\*This imputation will be done within two groups of randomised treatment arms.

\*\*Baseline refers to treatment baseline.

